8.8. Health Economics

Health economics/medical resource utilization and health economics parameters are not evaluated in this study.

9. STATISTICAL CONSIDERATIONS

Detailed methodology for summary and statistical analyses of the data collected in this study is outlined here and further detailed in a SAP, which will be maintained by the sponsor. The SAP may modify what is outlined in the protocol where appropriate; however, any major modifications of the primary endpoint definitions or their analyses will also be reflected in a protocol amendment.

9.1. Statistical Hypotheses

There is no formal statistical hypothesis testing in this study.

9.1.1. Estimands

9.1.1.1. DLT

Primary Estimand: DLT rate estimated based on data from DLT-evaluable participants during the DLT-evaluation period (Cycle 1) in Part 1.

- Variable: Occurrence of DLTs. DLTs are defined in [Section 4.3.3](#).
- Analysis population: DLT-evaluable participants defined as participants who receive at least 1 dose of study treatment, and either 1) received at least 75% of the planned doses of the study intervention and have received all scheduled safety assessments during the DLT-observation period or 2) have experienced a DLT regardless of the percentage of planned doses received. Participants without DLTs who withdraw from study treatment in the DLT-evaluation period for reasons other than treatment-related toxicity are not evaluable for DLT. All participants deemed non-evaluable for DLT may be replaced.
- Population-level summary measure: DLT rate defined as the number of DLT-evaluable participants with DLTs in the DLT-evaluation period divided by the number of DLT-evaluable participants in the DLT-evaluation period.

9.1.1.2. Incidence of AEs

Primary Estimand: Incidence of AEs estimated in the analysis population during the AE-evaluation period, defined as the time from the first dose to earliest of (28 days post last dosing date and day of new anti-cancer therapy -1 day).

- Variable: Occurrence of AEs. AEs are defined in [Appendix 3 Section 10.3](#).
- Analysis population: Safety analysis set defined as participants who receive at least 1 dose of study treatment without regard to tolerability or duration of treatment.
- Population-level summary measure: Incidence of AEs defined as the number of participants with AEs in the AE-evaluation period divided by the number of participants in the analysis population. AEs will be summarized by type, frequency, severity (as graded by NCI CTCAE version 5.0), timing, seriousness, and relationship to treatment.

9.1.1.3. OR

Estimand: The treatment effect of PF-07265028 in combination with sasanlimab assessed by ORR using the RECIST version 1.1 and irRECIST in the analysis population.

- Variable: Objective response defined as CR or PR according to RECIST v1.1 and irRECIST, from the date of first dose until the date of the first documentation of PD, death, or start of new anticancer therapy. Both CR and PR must be confirmed by

repeat assessments performed no less than 4 weeks after the criteria for response are first met.

- **Analysis population:** The response evaluable set defined as all enrolled participants who received at least 1 dose of study treatment and had adequate baseline disease assessment. Participants who discontinued early or died will be included.
- **Population-level summary measure:** ORR defined as the proportion of participants in the analysis population with OR and 2-sided 95% CI for ORR using the Clopper-Pearson/Wilson method. Participants who do not have a post-baseline tumor assessment due to early progression of disease, who receive anti-cancer therapies other than the study treatments prior to reaching a CR or PR, or who die, have PD, or stop tumor assessments for any reason prior to reaching a CR or PR will be counted as non-responders in the assessment of OR.

9.2. Analysis Sets

For purposes of analysis, the following analysis sets are defined.

Participant Analysis Set	Description
FAS	All enrolled participants who have been assigned to treatment. Participants are analyzed according to the treatment they were assigned.
SAS	All enrolled participants who receive at least 1 dose of study treatment. Unless otherwise specified the safety analysis set will be the default analysis set used for all analyses.
Per-Protocol Analysis Set (DLT-Evaluable Set)	All enrolled participants who had at least 1 dose of study treatment and either experienced DLT or do not have major protocol deviations during the DLT observation period.
mITT Population	All enrolled participants who have received at least 1 dose of study medication; have a baseline assessment and at least 1 post-baseline assessment.
PK Parameter Set	All enrolled participants treated who do not have protocol deviations influencing PK assessment, and have sufficient information to estimate at least 1 of the PK parameters of interest.
PK Concentration Set	All enrolled participants who are treated and have at least 1 analyte concentration above the lower limit of quantitation.
Response Evaluable Set	All enrolled participants who received at least 1 dose of study treatment and had adequate baseline disease assessment. Participants who discontinued early or died will be included.
Pharmacodynamic/ Biomarker Analysis Sets	The Pharmacodynamic/Biomarker analysis population is defined as all enrolled participants with at least 1 of the Pharmacodynamic/Biomarkers evaluated at pre- and/or postdose.
Immunogenicity Analysis Set	The immunogenicity analysis set is a subset of the safety analysis set and includes participants who have at least 1 analyzed sasanlimab ADA/NAb sample.

9.3. Statistical Analyses

The SAP will be developed and finalized before any analyses are performed and will describe the analyses and procedures for accounting for missing, unused, and spurious data. This section is a summary of the planned statistical analyses of the primary and secondary endpoints.

9.3.1. General Considerations

The data will be summarized with respect to demographic and baseline characteristics, efficacy observations and measurements, safety observations and measurements, PK, immunogenicity measurements, and biomarker measurements.

9.3.2. Primary Endpoints

For Part 1, determination of MTD will be performed using the Per-Protocol analysis set (evaluable for MTD).

For Part 2, the response evaluable set will be used for all response-related analysis, including ORR and DoR. See more details in [Section 9.3.3](#).

Bayesian adaptive approach:

The dose escalation in the Part 1 of the study will be guided by a Bayesian analysis of Cycle 1 DLT data for PF-07265028. A traditional 2-parameter BLRM will be used to model the DLT relationship of PF-07265028 monotherapy, and a more complex BLRM model specifically designed for combinations will be used to model the dose toxicity relationship of PF-07265028 given in combination with sasanlimab. Using DLT data at all tested dose levels and pre specified prior distribution of model parameters, the posterior distribution for probability of having a DLT will be calculated for all dose levels.

Assessment of participant risk:

After each cohort of participants, the posterior distribution for the risk of DLT for new participants at different doses of interest for PF-07265028 monotherapy and combination therapy will be evaluated. The posterior distributions will be summarized to provide the posterior probability that the risk of DLT lies within the following intervals:

- Underdosing: [0, 0.16];
- Targeted dosing: [0.16, 0.33];
- Overdosing: [0.33, 1].

The EWOC principle:

Dosing decisions are guided by the escalation with overdose control principle.¹ A dose may only be used for newly enrolled participants if the risk of excessive toxicity at that dose is less than 25%.

Prior distributions:

Weakly informative prior distributions based on preclinical/expert opinion information will be chosen for the logistic parameters, see [Appendix 11 Section 10.11](#).

A MAP approach may be used to derive the prior distribution for model parameters used in Part 1B based on the data collected in Part 1A and historical DLT data on sasanlimab as monotherapy. The MAP prior for the logistic model parameters for this study is the conditional distribution of the parameters given the historical data. MAP priors are derived from hierarchical models, which take into account possible differences between the studies. A full description of the application of the MAP approach to derive the prior distributions of the model parameters is given in Technical Supplement.

Starting dose:

The starting dose is 25 mg PF-07265028. For this dose the prior risk of overdosing is 7.1%, which satisfies the EWOC criterion. A full assessment of the prior risk to participants is given in [Appendix 11 Section 10.11](#).

Stopping criteria:

The number of participants in Part 1 dose escalation of the trial may be approximately 60. The trial for Part 1A and Part 1B will be stopped when the following criteria are met:

At least 6 participants have been treated at the MTD/RDE.

The dose \tilde{d} satisfies one of the following conditions:

- The probability of target toxicity at dose \tilde{d} exceeds 50%, ie, $\Pr(0.16 \leq \pi_{\tilde{d}} < 0.33) \geq 50\%$.
- A minimum of 12 participants have been treated for Part 1A, or a minimum of 9 participants have been treated for Part 1B.

Sensitivity analysis:

To mitigate the risk of dichotomizing and misclassifying DLTs, a sensitivity analysis that uses weighted DLT/AE data (in equivocal cases) into the BLRM model estimation will also be performed. If all the investigators and the sponsor agree on the equivocal DLT/AE data, the DLT weighting approach could be the primary dose escalation method. See [Appendix 11 Section 10.11](#) for more details.

9.3.3. Secondary Endpoints

The response evaluable set will be used for all response-related analysis, including ORR and DoR. Tumor response will be presented in the form of participant data listings that include, but are not limited to, tumor type, dose on Day 1, tumor response at each visit, and best overall response. In addition, progression date, death date, date of first response and last assessment date, and date of last contact will be listed. A summary of tumor response and best overall response based on RECIST 1.1 and irRECIST will also be presented.

The Kaplan-Meier method will be used to analyze time-to-event efficacy endpoints.

The detailed analyses will be described in the SAP.

9.3.3.1. Pharmacokinetic Analysis

9.3.3.1.1. Single Dose and Steady State PF-07265028 and Sasanlimab Pharmacokinetic Analysis (with the Exception of Food Effect Assessment)

The plasma concentration time data of PF-07265028 and serum C_{min} for sasanlimab will be summarized by descriptive statistics (n, mean, standard deviation, coefficient of variation, median, minimum, maximum, and geometric mean) according to dosing cohort and time for each part of the study. Exclusions or separate summaries for dose modifications and concomitant medications may be considered in data summaries.

In Part 1, following single dose administration of PF-07265028, plasma PK parameters including the C_{max} , T_{max} , AUC_{last} , AUC_{tau} and if data permit, AUC_{inf} , CL/F , V_z/F , and $t_{1/2}$ will be estimated. Following multiple doses of PF-07265028, steady-state PK parameters including $C_{max,ss}$, $T_{max,ss}$, $AUC_{last,ss}$, $AUC_{tau,ss}$, $C_{min,ss}$, CL_{ss}/F , and if data permit, V_{ss}/F , $t_{1/2}$, and R_{ac} ($AUC_{tau,ss}/AUC_{tau,sd}$) will be estimated. In Part 2 participants Not in food-effect subset, following multiple doses of PF-07265028, C_{min} will be reported. In Part 2 participants in food-effect subset, steady-state PK parameters including $C_{max,ss}$, $T_{max,ss}$, $AUC_{last,ss}$, $AUC_{tau,ss}$, $C_{min,ss}$, CL_{ss}/F under fasted and fed conditions will be estimated. In Part 1 and Part 2, following multiple doses of sasanlimab, C_{min} in selected cycles will be reported.

The single-dose and steady-state PK parameters will be summarized descriptively (n, mean, standard deviation, CV, median, minimum, maximum, geometric mean and its associated CV) by dose, cycle, and day.

Trough concentrations (C_{min}) will be plotted for each cohort using a box-and-whisker plot by cycle and day within cycle in order to assess the attainment of steady state. Dose normalized C_{max} , AUC_{last} , AUC_{tau} (at steady state) and AUC_{inf} (if estimated), and will be plotted against dose (using a logarithmic scale) by cycle and day. These plots will include individual participant values and the geometric means for each dose. These plots will be used to help understand the relationship between the PK parameters and dose.

9.3.3.1.2. Effect of Food on PF-07265028 Pharmacokinetics

For the evaluation of the food effect, PF-07265028 plasma concentration-time data will be compared on days taken under fasted (Reference) and fed conditions (Test). PK parameters ($C_{max,ss}$, $T_{max,ss}$, $AUC_{last,ss}$, $AUC_{tau,ss}$) of PF-07265028 given under fasted and fed conditions will be summarized descriptively. Natural log transformed AUC and C_{max} values will be analyzed using an analysis of variance model and treatment as fixed effects. Estimates of the mean differences (Fed-Fasted) and corresponding 90% CI will be obtained from the model. The mean differences and 90% CI for the differences will be exponentiated to provide estimates of the ratios of geometric means (Fed/Fasted) and 90% CI for the ratios.

9.3.3.2. Immunogenicity Analysis

For the immunogenicity data, the percentage of participants with positive ADA and Nab for each of sasanlimab combination dosing cohort will be summarized. For participants with positive ADA or neutralizing antibodies, the magnitude (titer), time of onset, and duration of ADA or neutralizing antibodies response will also be described, if data permit. The potential impact of immunogenicity on PK and CCI, safety/tolerability, and efficacy will be explored, if warranted by the data.

CCI

9.3.5. Other Safety Analyses

All safety analyses will be performed on the safety population.

AEs, ECGs, BP, pulse rate, cardiac monitoring results, and safety laboratory data will be reviewed and summarized on an ongoing basis during the study to evaluate the safety of participants. Any clinical laboratory, ECG, BP, and PR abnormalities of potential clinical concern will be described. Safety data will be presented in tabular and/or graphical format and summarized descriptively, where appropriate.

Medical history and physical examination and neurological examination information, as applicable, collected during the course of the study will be considered source data and will not be required to be reported, unless otherwise noted. However, any untoward findings identified on physical and/or neurological examinations conducted during the active collection period will be captured as AEs, if those findings meet the definition of an AE. Data collected at screening that are used for inclusion/exclusion criteria, such as laboratory

data, ECGs, and vital signs, will be considered source data, and will not be required to be reported, unless otherwise noted. Demographic data collected at screening will be reported.

9.3.5.1. Electrocardiogram Analyses

Changes from baseline for the ECG parameters QT interval, heart rate, QTcF, PR interval, and QRS complex will be summarized by treatment and time.

The number (%) of participants with maximum postdose QTcF values and maximum increases from baseline in the following categories will be tabulated by treatment:

Safety QTcF Assessment

Degree of Prolongation	Mild (ms)	Moderate (ms)	Severe (ms)
Absolute value	>450-480	>480-500	>500
Increase from baseline		30-60	>60

If more than 1 ECG is collected at a nominal time after dose administration (for example, triplicate ECGs, the mean of the replicate measurements will be used to represent a single observation at that time point. If any of the 3 individual ECG tracings has a QTcF value >500 ms, but the mean of the triplicates is not >500 ms, the data from the participant's individual tracing will be described in a safety section of the CSR in order to place the >500 ms value in appropriate clinical context. However, values from individual tracings within triplicate measurements that are >500 ms will not be included in the categorical analysis unless the average from the triplicate measurements is also >500 ms. Changes from baseline will be defined as the change between the postdose QTcF value and the average of the time-matched baseline triplicate values on Day -1, or the average of the predose triplicate values on Day 1.

In addition, an attempt will be made to explore and characterize the relationship between plasma concentration and QT interval length using a PK/pharmacodynamics modeling approach. If a PK/pharmacodynamics relationship is found, the impact of participant factors (covariates) on the relationship will be examined.

The analysis of ECG results will be based on participants in the safety analysis set with baseline and on-treatment ECG data. Baseline ECG is defined as the most recent ECG prior to Cycle 1 Day 1 dosing. ECG measurements (an average of the triplicate measurements) will be used for the statistical analysis and all data presentations. Any data obtained from ECGs repeated for safety reasons after the nominal time-points will not be averaged along with the preceding triplicates. Interval measurements from repeated ECGs will be included in the outlier analysis (categorical analysis) as individual values obtained at unscheduled time points.

QT intervals will be corrected for HR (QTcF) using standard correction factors (ie, Fridericia's (default correction), Bazett's, and possibly a study-specific factor, as appropriate). Data will be summarized and listed for QT interval, HR, RR interval, PR interval, QRS complex, QTcF (and other correction factors, eg, QTcB as appropriate), and by

dose. Individual QT (all evaluated corrections) intervals will be listed by time and dose. The most appropriate correction factor will be selected and used for the following analyses of central tendency and outliers and used for the study conclusions. Descriptive statistics (n, mean, median, standard deviation, minimum, and maximum) will be used to summarize the absolute value of the corrected QT interval and changes from baseline in corrected QT after treatment by dose and time point. Details of additional analysis (if any) will be specified in SAP.

9.3.5.2. AEs

AEs will be graded by the investigator according to the CTCAE version 5.0 and coded using MedDRA. AE data will be reported in tables and listings. Summaries of AE by appropriate MedDRA terms, toxicity grade, and seriousness and relationship to study treatment will be presented, as well as summaries of AEs leading to death and premature withdrawal from study treatment. The number and percentage of participants who experienced any AE, SAE, treatment-related AE, and treatment-related SAE will be summarized according to worst toxicity grades. Listings of DLTs and deaths will be provided.

9.3.5.3. Laboratory Test Abnormalities

The number and percentage of participants who experienced laboratory test abnormalities will be summarized according to worst toxicity grade observed for each laboratory assay. For laboratory tests without CTCAE grade definitions, results will be categorized as normal, abnormal, or not done.

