4.3.3. DLT Definition

A participant is classified as DLT-evaluable if the participant either 1) received at least 75% of the planned doses of the study intervention and have received all scheduled safety assessments during the DLT-observation period (Cycle 1 [28 days]) or 2) have experienced a DLT regardless of the percentage of planned doses received. The percentage of drug received is calculated as the percentage of the actual total amount of drug(s) administered during the DLT-observation period in relation to the planned total amount of drug(s) to be administered for the DLT-observation period. If a participant fails to meet these criteria, the participant is deemed non-evaluable for a DLT, and may be replaced. The sole exception to criterion 1 above is if the participant has missed a minority of safety assessments due to emergency situations (eg, site accessibility issues, inability to go to an external lab, etc). In such cases, the DLRM Committee may judge the participant evaluable, depending on the abundance of the available data.

For the purpose of dose escalation, all treatment-emergent AEs meeting the definition of DLT occurring in the first cycle of treatment (within 28 days of the first dose or until the participant receives the first dose of the second treatment cycle in the event of treatment delays) will be considered DLTs unless they are clearly attributable to underlying disease or intercurrent illness.

Severity of AEs will be graded according to CTCAE version 5.0. For those AEs involving a worsening of a baseline abnormality, a DLT must represent a clinically significant (in the opinion of the Investigator after discussion with the sponsor) shift from baseline.

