4.3.3.2. Non-Hematological DLTs

- Any treatment-emergent Grade >3 non-hematologic toxicity
- Hepatic toxicity events consistent with Hy's Law, ie,
 - >3-fold elevations above the ULN of ALT or AST AND
 - >2 × ULN elevation of serum total bilirubin without alternative explanation (eg, cholestasis or Gilbert's syndrome) AND
 - Absence of initial findings of cholestasis (eg, elevated serum ALP) AND
 - Absence of other reason(s) to explain the combination of increased ALT or ALP and TBili, such as viral hepatitis A, B, or C; preexisting or acute liver disease; or another drug capable of causing the observed injury.
- For participants with Grade 2 hepatic transaminase or alkaline phosphatase levels at baseline as a result of liver metastasis or bone metastasis, a hepatic transaminase or alkaline phosphatase level >10 × ULN.
- Grade 3 fatigue lasting ≥5 days.
- Grade ≥3 nausea/vomiting or diarrhea lasting ≥3 days despite adequate anti-emetic and other supportive care.
- Grade ≥3 CRS of any duration.

- Grade 3 QTcF prolongation:
 - In an asymptomatic participant, the following assessment and confirmation procedure is required: repeat testing, reevaluate by a qualified person, and correct reversible causes (such as electrolyte abnormalities or hypoxia). If, after correction of any reversible causes, the Grade 3 QTcF prolongation persists, then the event should be considered a DLT.
- Any Grade 4 QTcF prolongation.
- Treatment-emergent AEs resulting in failure to deliver 75% of doses of the first cycle doses of PF-07265028 and sasanlimab.
- Grade 5 event unless attributed to a cause clearly not related to study treatment.

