8.2.5. Clinical Safety Laboratory Assessments

See [Appendix 2](#) for the list of clinical safety laboratory tests to be performed and the [SoA](#) for the timing and frequency. Confirmation of eligibility is required at Cycle 1 Day 1. All protocol-required laboratory assessments, as defined in [Appendix 2](#), must be conducted in accordance with the laboratory manual and the [SoA](#). For laboratory collection volumes see the laboratory manual. Unscheduled clinical laboratory measurements may be obtained at any time during the study to assess any perceived safety issues.

The investigator must review the laboratory report, document this review, and record any clinically relevant changes occurring during the study in the AE section of the CRF. Clinically significant abnormal laboratory findings are those which are not associated with the underlying disease, unless judged by the investigator to be more severe than expected for the participant's condition.

All laboratory tests with values considered clinically significantly abnormal during participation in the study or within 30 days (± 7 days) after the last dose of study intervention should be repeated until the values return to normal or baseline or are no longer considered clinically significant by the investigator or medical monitor.

If such values do not return to normal/baseline within a period of time judged reasonable by the investigator, the etiology should be identified and the sponsor notified.

See [Appendix 6](#) for suggested actions and follow-up assessments in the event of potential drug-induced liver injury.

No need to repeat a clinical laboratory assessments on Cycle 1 Day 1 if the baseline assessment was performed within 7 days prior to that date ([SoA](#)).

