3. ENDPOINTS AND BASELINE VARIABLES: DEFINITIONS AND CONVENTIONS

3.1. Part 1 Primary Endpoints

- *First cycle DLTs.*
- *Adverse events (including irAEs) as characterized by type, frequency, severity (as graded by NCI CTCAE version 5.0), timing, seriousness, and relationship to study therapy.*
- *Laboratory abnormalities as characterized by type, frequency, severity (as graded by NCI CTCAE version 5.0), and timing.*

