6.1.3. Laboratory abnormalities

- Analysis set: Safety analysis set.
- Analysis methodology:

Laboratory tests in this study include several panels: hematology, chemistry, serology, coagulation, urinalysis, and pregnancy test.

The frequency and percentage of participants who experienced laboratory test abnormalities will be summarized according to worst toxicity grade (based on NCI CTCAE version 5.0) observed for each laboratory assay. Summaries of laboratory

tests results by visit may be provided. Summaries for change from baseline and percent change from baseline for the laboratory tests may be provided, if deemed necessary. Shift tables may be provided for selected laboratory tests.

The summaries will be presented for the entire on-treatment period and for the various parts of the study (by dose level for Parts 1A and 1B, by arm for Part 2), and will not be presented by treatment cycle.

Hematology, serology, and coagulation lab results can be combined into one summary output. Separate summaries will be created for chemistry tests. Urinalysis and pregnancy tests will not be summarized and will only be listed in data listings. Shift tables may be provided for selected laboratory tests.

- Missing data: Intermediate missing values (ie, values collected between baseline and the last study measurement) will not be imputed.

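### The only required table for the primary laboratory endpoint ignores the baseline grade, so unchanged entry abnormalities in blood counts, above all lymphocytes, are counted as on-treatment abnormalities

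*Protocol*

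**What the plan says.** SAP 3.1 lists among the Part 1 primary endpoints: "Laboratory abnormalities as characterized by type, frequency, severity (as graded by NCI CTCAE version 5.0), and timing". SAP 3.4 and Protocol 3.2 do the same for Part 2.

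The counting rule is in Protocol 9.3.5.3: the number and percentage of participants with abnormal tests "will be summarized according to worst toxicity grade observed for each laboratory assay". SAP 6.1.3 repeats the worst-grade rule and sets the window: "The summaries will be presented for the entire on-treatment period". Neither section requires the grade to be new or worse than at entry, and neither defines a treatment-emergent laboratory abnormality. The SAP's treatment-emergent definition (6.1.2) covers adverse events only.

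Displays that refer to baseline are optional. On shift tables SAP 6.1.3 says: "Shift tables may be provided for selected laboratory tests". Change-from-baseline summaries in the same section are likewise left to need.

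Elsewhere the plan does use a reference value. Protocol 4.3.3 states: "For those AEs involving a worsening of a baseline abnormality, a DLT must represent a clinically significant" shift from baseline. ECG changes from baseline are required (Protocol 9.3.5.1, SAP 6.1.5). SAP 3.7 and 5.2 define baseline as the last value before the first dose.

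**The concern.** The endpoint is meant to show what treatment does to laboratory values at each dose level and in each expansion arm. A worst-grade count with no baseline condition mixes two quantities: the share of participants who came in with the abnormality, and the share who developed it on study.

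This matters because abnormal entry values are expected. Protocol 5.1 admits hemoglobin just above 9 g/dL and platelets just above 100,000/µL, and sets no numeric limit for lymphocytes. Yet Protocol 2.2.7 names decreased circulating lymphocytes among the key toxicities of potential clinical importance, and absolute lymphocytes are in the core laboratory panel (Protocol 10.2, Table 14). The laboratory signal of most interest is therefore the one least separated from background. A study report could follow the plan to the letter and never show how much of an abnormality rate was there before dosing.

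**Working it through.** **No plan figure to reproduce.** The documents give no laboratory abnormality rate, so the check compares texts and then adds an illustration.

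**Step 1: which assays and grades can be affected.** Entry limits are from Protocol 5.1, Grade 3 cut-offs from Protocol 6.5.1, Table 11.

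| Assay | Entry limit | Grade ≥3 cut-off | Carry-over possible at |
|---|---|---|---|
| Hemoglobin | >9 g/dL | <8 g/dL | Grades 1-2 only |
| Platelets | >100,000/µL | <50,000/µL | Grades 1-2 only |
| Neutrophils | ≥1,500/µL | <1,000/µL | below Grade 3 only |
| Lymphocytes | none | not given in the documents | possibly any grade |

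The first three cut-offs are absolute, so a stable abnormal value keeps its grade and is counted. I assume the same for lymphocytes, whose grading limits the documents do not reproduce.

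**Step 2: liver tests.** The hepatic table in Protocol 10.3.5 gives AST, ALT and bilirubin grades as multiples of baseline when baseline was abnormal; Grade 1 for AST or ALT starts above 1.5 times baseline. A participant who enters at 4 x ULN with liver metastases and stays there has a ratio of 4/4 = 1.0 and is not graded. These tests are largely exempt. That table does not cover alkaline phosphatase, so I make no claim about it.

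**Step 3: illustration of size, any grade.** Let *b* be the share who enter with the abnormality and keep it, and *t* the share with a new or worsened abnormality, taken as independent of *b*. Both are assumptions.

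- Worst-grade table shows: b + (1 − b)t
- Treatment-emergent count shows: t
- Excess: b(1 − t)

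With t = 20%:

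| b | Worst-grade table | Treatment-emergent | Excess |
|---|---|---|---|
| 10% | 0.10 + 0.90 × 0.20 = 28% | 20% | 8 points |
| 20% | 0.20 + 0.80 × 0.20 = 36% | 20% | 16 points |
| 40% | 0.40 + 0.60 × 0.20 = 52% | 20% | 32 points |

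In a full Part 2A cohort of 40 this is an expected 11.2, 14.4 or 20.8 participants shown as abnormal, against 40 × 0.20 = 8 with a new or worsened abnormality. With t = 0 the worst-grade table shows b itself, and the treatment-emergent count shows 0%.

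**The case against.** The strongest reply is that decisions are protected elsewhere, and most of it stands. Escalation runs on DLTs, and a DLT on a pre-existing abnormality needs a clinically significant shift. The protocol also foresees abnormal liver values at entry with a separate rule: "For participants with Grade 2 hepatic transaminase or alkaline phosphatase levels at baseline as a result of liver metastasis or bone metastasis". Clinically significant laboratory worsening is recorded as an adverse event (Protocol 10.3.1) and enters the required adverse event tables. The study tests no hypothesis. For hemoglobin, neutrophils and platelets the Grade 3-4 counts are clean, because eligible participants cannot start there and a fall to Grade 3 still shows as Grade 3. For lymphocytes, inclusion criterion 13 requires acute effects of prior therapy to have resolved to baseline severity or Grade ≤1, but it allows exceptions at the investigator's discretion and is not a numeric limit.

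Four stronger readings are tempting, and the documents do not support them.

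- *Baseline values may be missing from the report.* Protocol 9.3.5 says that screening laboratory "data, ECGs, and vital signs, will be considered source data, and will not be required to be reported, unless otherwise noted", and Protocol 8.2.5 says: "No need to repeat a clinical laboratory assessments on Cycle 1 Day 1 if the baseline assessment was performed within 7 days". A reader might infer that the only pre-dose value of some participants drops out. But the rule carries its own exception, not having to report is not the same as not collecting, and SAP 3.7 and 5.2 make the last pre-dose value the baseline. The same sentence covers ECGs, whose change from baseline is required. This needs clarifying and is not a defect.
- *High and low abnormalities are pooled.* Counting by assay leaves this open, but neither document says that directions are combined.
- *Chance differences between small dose groups show the harm.* Two groups of 6 with a 20% rate differ by 2 or more participants in 26.7% of comparisons. That holds equally if the 20% is a true treatment-emergent rate, so it is small-sample noise that a baseline condition would not remove.
- *Escalation is distorted.* It is not, for the reason given above.

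**Conclusion.** The point holds in a limited form. For this primary endpoint, the only table the plan requires cannot separate entry status from change on treatment for assays graded on absolute limits. The effect is confined to Grades 1-2 for hemoglobin and platelets, and may reach any grade for lymphocytes. It largely spares AST, ALT and bilirubin and does not touch the DLT-based dose decisions.

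The size cannot be fixed from the documents because they give no baseline prevalence. Under the assumed range of 10% to 40% persistent baseline abnormality and 20% true emergence, the any-grade rate is overstated by 8 to 32 percentage points. That range assumes full persistence of the entry abnormality and emergence unrelated to baseline status. It should be read as an illustration, not an estimate.

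**What to change.** In Protocol 9.3.5.3 and SAP 6.1.3:

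1. Add a count of treatment-emergent laboratory abnormalities: worst on-treatment grade higher than the baseline grade, or baseline missing. Count by CTCAE term, so that low and high directions are separate. The existing worst-grade table can stay beside it.
2. Make the table of baseline grade by worst on-treatment grade required for every CTCAE-gradable assay, by dose level in Part 1 and by arm in Part 2.

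As a clarification only, add to Protocol 9.3.5 that a screening value serving as the SAP baseline is used and reported as such.

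No new samples or visits are needed, since pre-dose laboratory tests are already scheduled. The cost is wording in two documents, a standard shift-table program and a few more table pages.
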